6.3.8.6 Growth parameters

At 2 years, we will measure head circumference, length, and weight.

6.3.8.7 Child Behavior Checklist (CBCL)

At 2 years, we will administer the CBCL, a parental questionnaire that includes 99 items that describe specific kinds of behavioral, emotional, and social problems. We will specifically evaluate the externalizing score for evidence of attention problems and aggressive behavior. This checklist will be scored centrally.

6.3.8.8 Warner Initial Developmental Evaluation of Adaptive and Functional Skills (WIDEA)

The WIDEA is a questionnaire developed and standardized to assess the 4 functional domains of self-care, motor function, communication, and social cognition in young children. Normative data are available for this instrument through 36 months of age. [name] (follow-up PI) will provide an interactive WIDEA video training session and certification for study personnel who will administer this parental questionnaire.^{121,122}

6.3.9 Extended Contact Phone Calls

At the 24-month study visit, or by phone after the visit has been completed, the parent/guardian should be approached for consent for participating in Extended Contact phone calls. If consent is obtained, these calls should be performed at the following intervals:

- 30 months (± 56 days)
- 36 months (± 56 days)
- 42 months (± 56 days)
- 48 months (± 56 days)
- 54 months (± 56 days)
- 60 months (± 56 days)
- 66 months (± 56 days)
- 72 months (± 56 days)
- 78 months (± 56 days)
- 84 months (± 56 days)
- 90 months (± 56 days)

- 96 months (± 56 days)

These phone calls will be used to maintain relationships with participating families, ensure updated contact information is on file, and to gather basic information about how the child is doing. The WIDEA may be performed at the 30- and 36-month calls. Data may be used to support future applications for follow-up studies on this population.

Failure to complete these follow-up calls, or performing these follow-up calls outside of the requested windows, does not constitute a study deviation.

Any deaths identified during these Extended Contact phone calls must be reported as SAEs.

7 MANAGEMENT OF SERIOUS ADVERSE EVENTS AND COMPLICATIONS OF HIE

The study will be monitored by a **NINDS-appointed DSMB** with independent experts in the areas of pediatric neurology, neonatology and biostatistics. The study will be monitored for safety by the DSMB with reviews for enrollment, follow-up, data quality, overall study conduct, participant safety, and significant adverse event rates. Meeting frequency and conduct will be detailed separately by the DSMB. For this NINDS grant, the DSMB will follow the guidance presented in the NINDS Guidelines for Data and Safety Monitoring:

http://www.ninds.nih.gov/research/clinical_research/policies/data_safety_monitoring.htm

A neonatologist who is independent of the study will serve as the **Medical Monitor**, and will monitor all serious adverse events concurrently. The Medical Monitor will be masked to treatment allocation.

7.1 SERIOUS ADVERSE EVENT DEFINITIONS

In the HEAL study, the following events, occurring within 30 days of study drug dosing, will be reported as Serious Adverse Events (SAEs). Death occurring any time during the neonatal or follow-up period will always be reported as an SAE.

- **Systemic hypertension**
 - Definition: If blood pressure is elevated enough to require antihypertensive therapy
- **Polycythemia**
 - Definition: Central hematocrit (Hct) > 65.0%, as measured by a central lab on 2 consecutive free-flowing arterial or venous samples.
(Note: High Hct values measured by point of care tests are not sufficient for meeting polycythemia criteria for purposes of this study)
- **Disseminated intravascular coagulation (DIC)**
 - Clinical bleeding or oozing requiring transfusion of blood products (e.g., FFP, cryoprecipitate or platelets)
(Note: Laboratory findings may include elevated INR, PTT, PT, or D-dimers, or low PLT or fibrinogen)
- **Major venous or arterial thrombosis (clot): Definition = any of the following 3:**
 - Any thrombosis that is treated with a course of anticoagulation
 - Any venous or arterial thrombosis involving a major vessel **not** related to a central line

- Any **symptomatic** thrombosis involving a major vessel (e.g., symptoms such as superior vena cava syndrome)
- **Pulmonary hypertension**
 - Elevated pulmonary vascular resistance treated with inhaled nitric oxide or ECMO therapy
- **Intracranial hemorrhage**
 - Intraparenchymal or intraventricular blood visualized by HUS or MRI T1 or T2 sequences
- **Cardiopulmonary arrest**
 - Clinical code event requiring chest compressions or epinephrine bolus from which the infant recovers (does not lead to death), that is not secondary to endotracheal tube (ETT) obstruction or other mechanical issue
- **Other unexpected life-threatening event**
 - Unexpected for HIE, or unexpected based on the Epo drug profile
- **Death**

The definition for an SAE in our population of HIE newborns is consistent with 21 CFR 312.21 (2005).

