9.6 DATA AND SAFETY MONITORING PLAN (DSMP)

The DSMB will review the accruing data to: 1) ensure that the study is adequately enrolling; 2) to ensure that there are no serious safety concerns; and 3) to assess whether the study efficacy appears overwhelming. The DSMB will be assigned by NINDS. The research coordinator at each site will monitor each subject weekly for the presence of any complications. Serious adverse events will be brought to the attention of the DSMB, and if appropriate, the IRB, in writing. An independent medical monitor will review all cases of serious adverse events.

As part of this DSMP, we will perform continuous and interim analysis of accruing safety data. We have defined potentially treatment (Epo) related serious adverse events (SAEs) that will be monitored throughout the course of the study. Specifically, for SAEs we will compare absolute rates to expected rates based on published data for similar newborns, and will seek careful DSMB review and guidance when observed rates exceed pre-specified thresholds. In addition, at planned interim analysis we will formally compare the event rates across the two treatment groups using appropriate small sample methods such as Fisher's exact test. The DCC PI will remain masked to assignment while the study staff statistician will not.

The primary outcome of the study is a composite endpoint of mortality or NDI at 24 months of age. Therefore, monitoring the primary outcome for treatment efficacy or futility is challenging. Based on enrollment plans, the majority of patients will have been randomized by the time NDI is assessed at 24 months for any participants, and therefore we do not expect to be able to conduct a first interim analysis prior to the completion of enrollment. We expect to have the primary outcome evaluated on the first quarter of subjects (n=125) after 34 months of recruitment at which point we expect to have randomized n=450 of the total n=500 subjects (90% enrollment completed). Therefore, any actions that a DSMB might take to prevent subsequent patients from receiving an ineffective treatment (futility) or to make available a useful treatment (efficacy) will not have a direct impact on patients participating in

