this study. As a surrogate for long-term 24-month clinical efficacy on NDI, one alternative would be to monitor directly early MRI results as intermediate outcomes or surrogates. However, a large study published by Cheong et al.,¹⁵⁰ found that early MRI measurements had poor sensitivity (27-60%) for accurately predicting death or NDI at 2 years. Therefore, we do not recommend using early MRI measures as a surrogate for the long-term outcome for monitoring treatment efficacy. Given that we are not conducting interim analysis directly on the primary outcome measure for efficacy or futility, we do not make adjustments to sample size or statistical power to account for interim alpha spending.

Our primary objective for interim analyses is therefore to allow for careful and continued monitoring of mortality and safety outcomes. We propose to conduct formal statistical analysis and inference for mortality at three interim and one final analysis time. We will continue to present mortality and SAE data from all available follow-up data, but we expect most treatment-related safety events to occur within the first three months of follow-up. We will conduct formal safety evaluation at 6, 12, 18, and 24 months following the start of enrollment, where approximately 25, 50, 75, and 100% of the study cohort will have been randomized and followed for at least 3 months. As part of each interim analysis, we plan to monitor mortality as a primary safety endpoint and will control the overall significance level using O'Brien-Fleming boundaries (net alpha=0.05 significance, accounting for three interim and one final analysis). The DSMB will also monitor all other SAEs utilizing the same O'Brien-Fleming sequential monitoring boundaries without further adjustment for multiple comparisons, but allowing for flexibility to continue the study if the O'Brien-Fleming boundary is reached on a secondary SAE endpoint.

Table 11. O'Brien-Fleming Monitoring Boundaries

Enrollment	Monitoring p-value: Death
25%	0.000014734
50%	0.0030359
75%	0.016248
100%	0.030701

EXAMPLE SAFETY MONITORING TABLE

Shell Table 1. Closed Report: Serious adverse event (SAE) incidence rate (number of events/number at risk) and threshold for action.

Serious Adverse Events	Group A	Group B	Expected (Range)	Threshold for Action	p-value*
Systemic hypertension			0.2-3.0 ¹⁵¹⁻¹⁵³	6%	
Polycythemia			1.0-5.0% ¹⁵⁴	10%	
Disseminated intravascular coagulation (DIC)			11.0-45.0% ³⁻⁷	50%	

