## 5.5 Safety Data

Clinical safety data includes serious adverse events (SAEs) and clinical laboratory markers both from the hospitalization and study intervention period and from the long-term follow-up period. Because these are critically ill newborns, we anticipate that most safety events will occur during the initial inpatient and treatment period. Safety event rates will be tabulated by study group and compared separately for each SAE using a multivariable logistic regression model, with adjustment for randomized treatment group, and randomization stratification factors of clinical recruitment site and HIE severity (moderate/severe). We will additionally create a per-patient aggregate count of SAEs and evaluate the rates between groups using a Poisson regression model with robust standard errors and adjustment for randomization stratification factors. For any safety events that occur infrequently (<2%), we will use Fisher's exact test to compare the rates between treatment groups. All safety events identified post-birth will be included in the primary analysis, while the secondary analyses will evaluate safety events occurring post-treatment with the first study drug dose as well as those events assessed as being possibly related to the study drug. Statistical significance is defined conservatively at the alpha=0.05 level with no correction for multiple outcomes.

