## 9. Data and Safety Monitoring Plan (DSMP)

An NINDS-appointed independent Data and Safety Monitoring Board (DSMB) will review the accruing data to: 1) ensure that the study is adequately enrolling; 2) to ensure that there are no serious safety concerns; and 3) to assess whether the study efficacy appears overwhelming. The DSMB will be assigned by NINDS. The research coordinator at each site will monitor each subject weekly for the presence of any complications. Serious adverse events will be brought to the attention of the DSMB, and if appropriate, the IRB, in writing. An independent medical monitor will review all cases of serious adverse events.

As part of this DSMP, we will perform continuous and interim analysis of accruing safety data. We have defined potentially treatment (Epo) related serious adverse events (SAEs) that will be monitored throughout the course of the study. Specifically, for SAEs we will compare absolute rates to expected rates based on published data for similar newborns and will seek careful DSMB review and guidance when observed rates exceed pre-specified thresholds. The following SAEs will be prospectively reviewed by the DSMB:

- Systemic hypertension requiring treatment
- Polycythemia (hematocrit > 65%)
- Major venous or arterial thrombosis (clot)
- Disseminated Intravascular Coagulation (DIC)
- Pulmonary Hypertension
- Intracranial Hemorrhage

- Cardiopulmonary Arrest
- Death
- Other unexpected life-threatening event (unexpected for HIE or Epo drug profile)

In addition, at planned interim analysis we will formally compare the event rates across the two treatment groups using appropriate small sample methods such as Fisher's exact test. The DCC PI will remain masked to assignment while the study staff statistician will not.

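### Cardiopulmonary arrest counts as that SAE only if the infant survives it, so the by-arm arrest comparison depends on survival and no planned table counts all arrests

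*Protocol*

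**What the plan says.** Protocol 7.1 lists the SAEs. Its arrest entry is a "Clinical code event requiring chest compressions or epinephrine bolus from which the infant recovers (does not lead to death"), with arrests of mechanical cause excluded. No other event on the list carries a survival condition. A fatal arrest falls under a separate entry: "Death occurring any time during the neonatal or follow-up period will always be reported as an SAE".

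SAP 9 gives the DSMB a list of SAEs to review. There the event appears only as "Cardiopulmonary Arrest", with no definition and no survival restriction. SAP 5.5 says of the analysis: "Safety event rates will be tabulated by study group and compared separately for each SAE using a multivariable logistic regression model". Events below 2% go to Fisher's exact test, and a per-patient SAE count is analysed by Poisson regression.

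Protocol 9.6 says of SAE rates that the team "will seek careful DSMB review and guidance when observed rates exceed pre-specified thresholds". Example Shell Table 1 gives arrest an expected rate of 0.002-0.13% and an action threshold of 5%. Death has 8.1-35.1% and 40%. Protocol 9.6 also says "we plan to monitor mortality as a primary safety endpoint and will control the overall significance level using" O'Brien-Fleming boundaries, and of the remaining events "The DSMB will also monitor all other SAEs utilizing the same" boundaries.

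**The concern.** Survival after an arrest is a post-randomization outcome that treatment could change. An event counted only when the infant survives mixes how often arrests occur with how often they kill. The by-arm comparison then does not estimate the effect of Epo on arrest, and it errs in the reassuring direction when Epo makes arrests more lethal.

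Arrest is a reasonable harm to want measured cleanly. Protocol 2.2.2 lists myocardial infarction, thrombosis and increased death among effects reported in adults. It also says these were seen with long-term therapy and have not been reported in neonates.

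The definition also leaves a case open. An infant who is resuscitated and dies days later may or may not have recovered from an arrest that did not lead to death. The site must judge the cause, and no time limit is given.

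**Working it through.** **Inputs from the documents.** 250 per arm (SAP 1.2); control mortality 14% (Protocol 9.4.1, SAP 7.1); arrest threshold 5% and expected rate 0.002-0.13%, death threshold 40% (Shell Table 1); printed final-look limit for death 0.030701 (Protocol Table 11, SAP Table 6). The 5% has no stated derivation, so there is no plan figure to reproduce.

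**Assumed.** True arrest incidence *a* and fatal share *L*. The documents give neither, so a range is shown.

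**1. Direction of the bias.** Reported arrest rate = *a*(1 − *L*). At equal *a*, Epo minus placebo = −*a*(*L*_Epo − *L*_placebo), which is negative whenever arrests are more lethal on Epo. With *L* = 30% on placebo and 60% on Epo:

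| True incidence, both arms | Row reads, placebo | Row reads, Epo |
|---|---|---|
| 2% | 1.4% | 0.8% |
| 4% | 2.8% | 1.6% |
| 6% | 4.2% | 2.4% |
| 10% | 7.0% | 4.0% |

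A real excess can also vanish. With 4% arresting on placebo (30% fatal) and 8% on Epo (65% fatal), the row reads 0.04 × 0.70 = 2.8% against 0.08 × 0.35 = 2.8%.

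**2. What the death comparison would see.** Added deaths at equal incidence = *a*(*L*_Epo − *L*_placebo). For the 6% row this is 0.06 × 0.30 = 1.8 points, all other deaths being equal. Power = Φ[(d − z·se₀)/se₁], with pooled se₀ and unpooled se₁. For d = 0.018: se₀ = √(0.149 × 0.851 × 2/250) = 0.0318, se₁ = √((0.14 × 0.86 + 0.158 × 0.842)/250) = 0.0318, z = 2.16, giving Φ(−1.60) = 0.055.

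| Added to 14% mortality | Power at p=0.0307 | Power at p=0.05 |
|---|---|---|
| +1.8 points | 6% | 8% |
| +3 | 11% | 15% |
| +5 | 26% | 32% |
| +10 | 76% | 82% |
| +11 | 83% | 88% |

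The doubled-arrest example adds 0.08 × 0.65 − 0.04 × 0.30 = 4.0 points, for 17% power at 0.0307. The 40% death threshold would need 40 − 14 = 26 points.

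**3. The 5% arrest threshold.** 5% of 250 is 12.5, so it is exceeded at 13 or more infants. P(X ≥ 13) for Binomial(250, *a*), counting all arrests:

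| True incidence | Chance of exceeding 5% |
|---|---|
| 1% or less | about 0 |
| 2% | 0.2% |
| 4% | 20% |
| 6% | 74% |
| 8% | 97% |

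As defined, 8% incidence with half fatal is recorded as 4%, and the chance falls from 97% to 20%. At the top of the Protocol's expected range, 250 × 0.0013 = 0.3 arrests per arm, and the threshold is out of reach under either definition.

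**4. The per-patient SAE count.** A survived arrest scores one event (arrest). An arrest that is immediately fatal scores one event (death). A shift from survived to fatal leaves the total unchanged.

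**The case against.** A reader might infer that a treatment making arrests more lethal would escape the DSMB. The documents do not support that. Death is always an SAE, with no time limit. It has its own row, is the primary safety endpoint under O'Brien-Fleming boundaries, and is part of the primary outcome. Fatal arrests therefore move to the most closely watched row. What remains is that this row has little power for shifts of a few points.

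A reader might also infer that deaths are never linked to a preceding arrest. That cannot be established, because the SAE form is not in the documents. Protocol 7.3 requires full documentation of every SAE within 7 days, and a Medical Monitor reviews all of them. What can be said is that no planned table counts all arrests.

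The illustrative rates are open to challenge. An incidence of 6% is about 46 times the top of the Protocol's expected range (6/0.13), and the fatal shares have no source. The reference cited for that range is titled as a review of sudden postnatal collapse in newborns, so it may not describe cooled HIE infants. That justifies a range, not a claim that arrests will be common. Even at 6%, 4.2% against 2.4% is about 10 or 11 infants against 6 (Fisher p 0.32 to 0.45), so the distortion would be a misleading table entry, not a significant finding.

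Shell Table 1 is headed as an example, and crossing a threshold triggers review, not stopping. Keeping the two terms exclusive also has a plausible purpose: one fatal code is not counted twice in the per-patient count. That can be handled by a counting rule.

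**Conclusion.** The point holds for the arrest row and the by-arm arrest comparison. Both are conditioned on survival. At equal incidence, the arm with more lethal arrests always shows fewer of them; this follows from the definition and needs no assumed rate. The SAP's unqualified listing adds a risk that readers take the row to mean all arrests.

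The size depends on assumptions. Apparent differences of 0.6 to 3.0 points arise for incidences of 2% to 10% with fatal shares of 30% and 60%. Mortality monitoring limits the harm but is a weak substitute: about 6% power for +1.8 points and 26% for +5 points, taking the printed 0.0307 as a p-value limit. Using 0.05 does not change that conclusion.

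The threshold effect is secondary. At 2% incidence or less, the 5% line is almost never crossed even when all arrests are counted (0.2% at most). The main gain from a change is a by-arm comparison that does not depend on survival.

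**What to change.** - Define and tabulate every non-mechanical code event that meets the compressions-or-epinephrine criterion, whatever its outcome, with fatal and survived arrests shown beneath the total. State how an infant who is resuscitated and dies later is classed in that split.
- Use the total for the SAP 5.5 arrest comparison and for the DSMB arrest row. Ask the DSMB to confirm that 5% is the threshold it wants for the total.
- Count a fatal arrest once in the per-patient SAE count.
- Put the same definition in Protocol 7.1, Shell Table 1 and SAP 9.

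Cost: a change of definition and table shells, and perhaps one yes/no item on the death SAE form asking whether a code event preceded the death. A fatal arrest would then appear under two terms in the by-term table, which a footnote can explain. Treatment and clinical management are not affected.

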7.2 SAE RELATEDNESS & SEVERITY

For all Serious Adverse Events (SAE, as noted above), the site investigator will use their best medical judgment and indicate whether the SAE is related to the research (i.e., related to any research procedure including but not limited to the main intervention). The investigator will assign the SAE to one of the four categories below:

- **Definitely related:** The SAE *is clearly related* to the intervention
- **Probably related:** The SAE *is likely related* to the intervention
- **Possibly related:** The SAE *may be related* to the intervention
- **Unlikely:** The SAE *is doubtfully related* to the intervention
- **Not related:** The SAE *is clearly NOT related* to the intervention

The investigator will also provide an SAE severity:

- **Mild:** asymptomatic or mild symptoms; clinical or diagnostic observations only; no intervention indicated
- **Moderate:** minimal, local, or noninvasive intervention indicated
- **Severe:** Severe or medically significant, but not immediately life-threatening; hospitalization or prolongation of hospitalization indicated; disabling
- **Life-threatening:** Life-threatening consequences; urgent intervention indicated

Medical Monitor	DSMB	
 ▪ Epo-related SAEs: within 15 calendar days after sponsor's initial receipt of the information 	
 ▪ Within 15 calendar days after sponsor's initial receipt of the information

**In some instances, the CCC and/or Medical Monitor may require more expeditious completion of the SAE form*

Figure 2. SAE and Unanticipated Related Drug Effects Reporting Timelines

7.4 ANTICIPATED MEDICAL COMPLICATIONS (ADVERSE EVENTS) IN HIE PATIENTS

Critically ill infants with HIE commonly experience multiple medical complications. Medical complications of HIE patients will be recorded on case report forms, entered into the portal, and analyzed to determine if they occur in different frequencies between the treatment and control groups.

7.5 CRITERIA FOR MODIFICATION OF INTERVENTION REGIMEN

7.5.1 Criteria for Withholding/Stopping the Study Drug

- Central HCT > 65.0%
- Systemic hypertension *requiring treatment* as determined by the clinical team.^{137,138}

7.5.2 Restarting Study Drug

- Study drug will be restarted when central HCT < 60.0%
- Study drug will be restarted when blood pressure is within the normal range for age for 48 hours, or normotensive on a stable dose of anti-hypertensives.
 - o If the study drug is held on Study Days 1-4, one held dose may be made up, as long as it is given >20 hours before and >20 hours after any other study drug doses, and before the Study Day 7 dose window.
 - o If the study drug is held on Study Day 7, the held dose may be made up any time though Study Day 10.
 - o Only one held dose may be made up, in total.
- Note that any per-protocol blood samples should be drawn at the protocol-specified times. Blood sample times are not adjusted in cases where study drug is held.

Open Label Use of Epo. Open label use of Epo is not permitted in enrolled infants during the initial neonatal hospitalization. It is very unlikely that open label Epo use will pose a problem, since standard treatment for acute anemia in term infants is red blood cell transfusion, and Epo is rarely (if ever) used in this clinical setting.

If study drug is discontinued in any subject, parents will be encouraged to continue to allow their child to participate in the follow-up evaluations.

